Clinical Investigation Protocol (incl. statistical considerations)

Clinical examination of the F-Composite 2 Systems in the direct filling therapy

(NCT03221660)

INDEX

1. OBJECTIVES AND HYPOTHESES OF THE CLINICAL INVESTIGATION	3
2. GENERAL OVERVIEW OF THE CLINICAL INVESTIGATION	4
3. JUSTIFICATION FOR THE STRUCTURE OF THE CLINICAL INVESTIGATION.....	4
4. INVESTIGATORS	5
5. MATERIALS	5
6. RISKS AND BENEFITS OF THE INVESTIGATIONAL PRODUCT AND THE CLINICAL INVESTIGATION	6
7. STRUCTURE OF THE CLINICAL INVESTIGATION.....	7
7.1 GENERAL INFORMATION	7
7.2 PRODUCTS AND REFERENCE PRODUCTS	8
7.3 PARTICIPANTS (IN-/EXCLUSION CRITERIA).....	9
7.4 TREATMENTS	10
7.5 SPECIFICATIONS FOR MONITORING	11
8. STATISTICAL CONSIDERATIONS	12
9. DATA MANAGEMENT.....	12
10. CHANGES TO THE CLINICAL INVESTIGATION PROTOCOL	13
11. DEVIATIONS FROM THE CLINICAL INVESTIGATION PROTOCOL.....	13
12. PROOF OF USE OF THE PRODUCT.....	13
13. DECLARATION OF CONFORMITY	13
14. PROCEDURE FOR OBTAINING CONSENT	14
15. ADVERSE EVENTS, ADVERSE EFFECTS OF THE PRODUCT AND PRODUCT DEFECTS..	14
16. POPULATION THAT CAN BE PRESSURED	14
17. PREMATURE TERMINATION OR SUSPENSION OF THE EXAMINATION	15
18. PUBLICATION POLICY	15
19. REFERENCES	15

1. Objectives and hypotheses of the clinical investigation

a) The aim of this prospective study is to evaluate the clinical performance of F-Composite 2, a proven flowable bulk material and adhesive system for the restoration of masticatory posterior fillings (Class I and II), all three materials being polymerized with Bluephase PowerCure (flash mode).

b) Primary hypotheses to be accepted or rejected by statistical data from the clinical investigation.

[name]. [name] from the Biostatistical Department of the Institute of Social and Preventive Medicine at the University of Lausanne, Switzerland, has performed a case number calculation. Assuming that a maximum of 10% post-operative hypersensitivity is acceptable, but actually only 5% is expected, the following formula can be used to calculate the case number (80% power, using a chi-square test at 5% probability of error)

$$N = (1.96 * \sqrt{0.95 * 0.05} + 0.84 * \sqrt{1 * 0})^2 / (1 - 0.95)^2 = 73 \text{ participants or fillings}$$

Furthermore, if one assumes - based on internal experience - that after one year there is a drop-out rate of 2%, 75 fillings are necessary at the beginning of the study to statistically confirm the primary endpoint (post-operative hypersensitivities).

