7.4 Treatments

a) Description of all treatments administered to the investigation participants during the clinical investigation Three operators place 25 fillings each.

Preparatory measures and cavity preparation

- A medical and dental anamnesis and detailed findings are taken for each patient and, if necessary, x-rays are taken. A visual analogue scale is used to record the preoperative complaints of the tooth to be restored with regard to temperature stimulus and bite sensitivity. However, no cold or bite sensation is set for this purpose. The vitality is checked with a cold spray. In addition, a therapy plan is drawn up in accordance with the restoration concept.
- A digital photo of the initial state is taken. The vestibular and oral views are printed out. The occurrence and extent of horizontal tears are drawn on it.
- If possible, rubber dams are used for drainage. If a rubber dam is not possible, an appropriate relative draining method is used (OptraGate, cotton rolls, saliva ejector).
- Then the insufficient filling or caries is removed.
- The preparations are done with 80 µm diamonds, a finish of the cavity edges with 25 µm diamonds. The cavity edges in the enamel are chamfered, but not gingivocervically.

Measurement of the cavity and renewed documentation of melt cracks

- A digital photo of the prepared cavity is taken
- The lowest point of the respective proximal boxes and occlusal pull-through is measured with a PA probe (Hu-Friedy PCPUNC 15) and documented on the CRF I. The reference for the proximal box is the proximal-occlusal cavity margin in the marginal ridge area and, for determining the occlusal pull-through depth, the occlusal cavity margin adjacent to the lowest point. The determination should be made with an accuracy of ± 1 mm.
- The average width of the cavity is given in absolute terms (accuracy ± 1 mm). The already mentioned periodontal probe is also used as an aid here.

- Prior to conditioning, the tooth is again examined for horizontal enamel cracks, which are recorded in the printed photographs in terms of their extent and localization and recorded on the CRF I. A cold-light fibre optic (light probe by Lercher) is used as an aid.
- The residual dentin thickness above the pulp is determined with a prepometer at the site with the lowest layer thickness (Wegehaupt et al. (2009)).

The partial matrix system from Garrison (Compositight) or Triodent (V3) is used as the matrix.

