7.5 Specifications for monitoring

This clinical investigation will be monitored by the sponsor at defined timely intervals. The Monitoring Plan lists the activities within the scope of monitoring.

8. Statistical considerations

- a) Due to the study design, no special statistical methods are necessary.
- b) The sample size is 75 fillings
- c) validity of the clinical investigation: the system is suitable for the market if the acceptance criteria are met.
- d) Expected drop-out rate: Analysis of older comparable studies show that an annual drop-out rate of 2% can be expected. Accordingly, three fillings could no longer be checked after 2 years.
- e) Acceptance criterion for post-operative hypersensitivity after 4 weeks: $\leq 10\%$ (=6 fillings).
Acceptance criterion for loss of vitality after 1 year: maximum 1 restored tooth
Acceptance criterion for filling replacement after 2 years: maximum 3 fillings
- g) If more than 50% of the patients suffer from postoperative hypersensitivity after placing at least 20 fillings, the study would be terminated.
- k) If patients discontinue the study or drop out for other reasons (including extraction of the tooth from a cause not related to the study, change of the opposing dentition or treatment by an external dentist), they are considered a drop-out and are reported separately with the drop-out cause (CRF V).
The recall data obtained up to the time of withdrawal from the study are used in the evaluation.

9. Data management

- a) Data verification is carried out with plausibility checks. The data is encrypted, since the patient names do not appear in the data tables, but the cases can be assigned using case numbers and patient IDs.
- c) The archiving of the data takes place on the company's secure servers. The data is stored as SPSS data sheets in anonymized form. The traceability is given by case numbers.
- d) The retention period of the data after completion of the study is 10 years.

Since all persons involved in the study, especially the operators and the evaluator, are familiar with and apply the company's internal guidelines regarding "Good Documentation Practice" (SOP-00081-EN; Good Documentation Practice), the traceability of changes is ensured by the dating and sizing of corrections.

CRFs, radiographs and clinical images will be collected as source data in this study.

Authorities and the Monitor will be granted access to the original data at any time, should this be necessary.

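### Section 8 e) equates ≤10% with 6 fillings, but for the planned 75 fillings ≤10% allows 7, so the primary criterion gives two answers at exactly 7 events

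*Combined protocol and SAP*

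**What the plan says.** All references are to the combined protocol and SAP.

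- Section 8 e), the primary criterion: "Acceptance criterion for post-operative hypersensitivity after 4 weeks: $\leq 10\%$ (=6 fillings"). The percentage and the count are joined by an equals sign.
- Section 8 b), the denominator: "The sample size is 75 fillings". Section 7.4 a) agrees: "Three operators place 25 fillings each".
- Section 8 c), the consequence: "the system is suitable for the market if the acceptance criteria are met".
- Section 8 a), the analysis: "Due to the study design, no special statistical methods are necessary".
- Section 8 k), drop-outs: "The recall data obtained up to the time of withdrawal from the study are used in the evaluation".
- Section 1 b) takes 10% as the acceptable maximum and 5% as the expected rate. It cites "80% power, using a chi-square test at 5% probability of error" and says that "75 fillings are necessary at the beginning of the study to statistically confirm the primary endpoint".
- Sections 1 (c) and 2 give the working hypothesis as at most 10% after one month, with no count.

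The figure of 6 fillings for this endpoint appears only in 8 e).

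**The concern.** The two halves of the criterion should be the same number, and for 75 fillings they are not. A result of exactly 7 affected fillings would satisfy one and fail the other. This is the primary endpoint of a single-arm study, and the stated decision rule compares the result with a fixed limit. If the governing form is not declared beforehand, someone would have to choose it after seeing the result, and market suitability is tied to the outcome.

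A second, smaller matter concerns how a pass is described. Section 1 b) speaks of statistical confirmation, whereas 8 e) compares an observed figure with a limit. That would be so whichever count were printed, and it affects only the wording of the claim.

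**Working it through.** **Inputs.** 75 fillings (8 b; 3 × 25 = 75 from 7.4 a); limit ≤10% and count 6 (8 e); expected rate 5% and acceptable maximum 10% (1 b); drop-out 2% per year, about three fillings after two years (8 d).

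**1. The plan's sample size reproduces.** The formula in 1 b) gives (1.96 × √(0.95 × 0.05) + 0)² / 0.05² = 72.99, so 73. Then 73 / 0.98 = 74.5, so 75. The denominator is not in doubt.

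**2. The count does not reproduce.** The largest count within 10% is the whole-number part of 0.10 × n.

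- n = 75: 7.5, so 7. Here 6/75 = 8.0%, 7/75 = 9.3% and 8/75 = 10.7%.
- n = 73 (before the drop-out allowance): 7.3, so 7.
- n = 72 (75 less the three losses expected by two years): 7.2, so 7.
- n = 70 to 79: always 7.
- n = 60 to 69: 6.

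Rounding 7.5 up or down does not give 6. To reach 60–69, between 6 and 15 of the 75 fillings (8–20%) would have to be lost by week 4, against a planned 2% per year.

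**3. Where the forms disagree.** With 75 fillings, 6 or fewer passes both forms and 8 or more fails both. Only 7 splits them.

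**4. How likely that is.** X is binomial with n = 75, fillings taken as independent; P(X = 7) = P(X ≤ 7) − P(X ≤ 6).

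| True rate | P(X ≤ 6) | P(X ≤ 7) | P(X = 7) |
|---|---|---|---|
| 5% | 91.9% | 96.6% | 4.7% |
| 8% | 60.6% | 75.0% | 14.4% |
| 10% | 36.7% | 52.1% | 15.4% |

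(Differences were taken before rounding, e.g. 0.7499 − 0.6064 = 0.1435 at 8%.)

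**5. What a pass shows.** The exact (Clopper-Pearson) two-sided 95% interval runs from the 2.5% quantile of Beta(x, 76 − x) to the 97.5% quantile of Beta(x + 1, 75 − x). It is 3.0–16.6% for 6/75 and 3.8–18.3% for 7/75. Both upper limits lie well above 10%.

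**The case against.** The best defence is that the intention is clear enough. The 10% limit appears in 1 b), 1 (c), 2 and 8 e); the count appears once, in brackets, as a gloss. A plain reader would take 10% as the rule and 6 as a slip. The stray figure is also the stricter one, so 6 or fewer satisfies both forms, and at the plan's own expected rate of 5% the disputed result has a probability of only 4.7%. This largely stands. It limits the size of the problem but does not remove it, because the line that states the criterion gives both forms and nothing ranks them.

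Three stronger readings are tempting, and the documents do not support them.

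- A reader might infer that the plan gives no clue to which number was meant. It does: the repeated 10% points to the percentage. What is missing is a statement that it governs.
- A reader might infer that missing the primary criterion by itself rules out market suitability. Section 8 c) says the system is suitable if the criteria are met. It does not say only if, so the negative conclusion is reasonable but unwritten.
- A reader might infer that accepting at a true rate of exactly 10% is an error of the rule. By the plan's own wording, 10% is within the limit.

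It can also be said that the confirmation wording and the power statement in 1 b) are a separate matter. That is right: they do not follow from 6 versus 7. They enter here only because the corrected line needs an accurate description.

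**Conclusion.** The criterion in 8 e) is wrong as written. For the planned 75 fillings, ≤10% means at most 7, not 6, and no denominator in the plan yields 6. The forms conflict at one result only, exactly 7 affected fillings, with probability 4.7% at a true 5% and 15.4% at a true 10%. Six is probably a slip, but no section says which form governs. Because this is the primary criterion and 8 c) ties market suitability to the acceptance criteria, it must be corrected.

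Meeting the criterion with 6 or 7 events would not confirm statistically that the rate is at most 10%, since the exact intervals reach 16.6% and 18.3%.

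The probabilities and intervals assume 75 evaluable, independent fillings. Up to two per patient are allowed, so some clustering is possible and would change these figures. The mismatch between 6 and 7 needs no such assumption.

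**What to change.** Before data are seen, state one governing form and its denominator in 8 e).

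- The form consistent with the rest of the plan is: observed proportion ≤10% of fillings evaluable at 4 weeks (at most 7 if 70–75 are evaluable). Making the proportion govern matters, because a fixed 7 would exceed 10% with 69 evaluable (7/69 = 10.1%).
- If the sponsor did intend 6 of 75 (8%), say so and change 1 b), 1 (c) and 2 to match. This lowers the chance of passing at a true 5% from 96.6% to 91.9%.

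Define evaluable at 4 weeks. Section 7.1 d) provides the extra examinations (14–20 or 30–35 days) only for patients with complaints, so state how fillings without such a visit are counted. Data obtained up to withdrawal stay in, as 8 k) provides.

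Report the proportion with an exact two-sided 95% confidence interval, describe the criterion as a point-estimate benchmark, and amend the confirmation wording in 1 b) accordingly.

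The cost is a few lines of text and one interval, with no new patients or data. The stated assurance becomes less favourable. Section 10 counts changes to objective criteria or statistical design as significant, so Ethics Committee approval may be needed first.

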(c) claimed and intended performance of the test product, which shall be demonstrated.

The following working hypotheses should be clarified:

- Teeth restored with the F-Composite 2 system have postoperative hypersensitivity in a maximum of 10% of cases after 1 month.
- A maximum of one tooth shows a loss of vitality within 12 months.
- With the selected application protocol, the F-Composite 2 system enables a filling quality at least comparable to F-Composite (see study "Clinical investigation of Flash Composite in direct restorative therapy" CEC-ZH No. 2011-0150/5.) After 2 years a maximum of 3 fillings should be replaced due to poor quality.

(d) The following risks shall be assessed:

- post-op discomfort. In almost all clinical studies with direct filling materials, postoperative hypersensitivity occurs in the range of a few percent of the treated teeth. Whether the probability of occurrence is increased when using the F-Composite 2 restorative system can only be estimated by a clinical study.

- Inflammation/death of the pulp (the "dental nerve"). In December 2015 a clinical study was completed after an observation period of three years (KEK-ZH No. 2011-0150/5), in which the filling material was polymerized with 10 000 mW/cm² for one second, but without exposing the adhesive to this light intensity. No permanent damage to the pulp due to the high light intensity or temperature gradient was observed. In addition, Bluephase PowerCure was used to investigate the temperature gradient in the pulp in in vitro studies on extracted teeth. The absolute temperature was comparable to other lamps (recorded in investigator's brochure). However, the temperature gradient was steeper.

- Cracks in the tooth structure or between tooth and restoration or marginal gaps which could lead to discoloration, secondary caries, filling fracture, filling loss or tooth fracture. In very severely hollowed cavities on extracted molar teeth with undercuts (worst-case scenario) under the cusps, horizontal cracks in the tooth structure could be observed in vitro in bulk fillings with the flowable composite (recorded in validation report examiner brochure). For this reason, special attention is also paid to this point during the clinical investigation.

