- Unexpected changes in the filling surface that could lead to roughness, discolouration or increased wear of the material. As the material is similarly polishable as a conventional composite material, it is expected that no more surface discolouration will be observed.

2. General overview of the clinical investigation

The F-Composite 2 system is a coordinated system of filling materials, adhesive and polymerization unit for direct restorative therapy in dentistry.

The aim of this single-arm prospective clinical study is to investigate the F-Composite 2 system in direct filling therapy of class I and II cavities.

The following working hypotheses should be clarified:

- Teeth restored with the F-Composite 2 system have postoperative hypersensitivity in a maximum of 10% of cases after 1 month, which corresponds to a frequency as described in the literature.
- With the selected application protocol, the F-Composite 2 system enables at least comparable restorative quality to F-Composite (see study "Clinical investigation of Flash Composite in direct restorative therapy" CEC-ZH No. 2011-0150/5.) After 2 years a maximum of 3 fillings should be replaced due to poor quality.
- The rate of loss of vitality after 1 year is maximum 1%, which corresponds to a frequency as described in the literature.

The clinical investigation will be conducted with a maximum of 75 patients. No more than two restorations will be placed in any one patient. For inclusion and exclusion criteria, see item "7.3 Participants".

Recalls take place after 6, 12, 24, 60 months.

Aftercare

At the end of the study period or when patients leave the study, they will continue to be routinely cared for by their private dentist.

3. Justification for the structure of the clinical investigation

In summary, it can be concluded from the literature cited in the investigator's brochure that restorative composites are suitable for the intended indications and show a clinically acceptable performance.

Up to now, polymerization of the adhesive or a composite increment takes 5 to 40 seconds, depending on the material used and the polymerization lamp used to cure the material. Currently, the upper limit of available light intensities for direct restorations is approximately 2'000 mW/cm². In a recent study from Norway (Kopperud et. al, 2017), in which 740 dentists from the public sector were interviewed, it was shown that these dentists exposed each composite increment for an average of 27 s.

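### The 1-year vitality and 2-year replacement limits are bare counts that ignore how many fillings were still examined, so they become easier to meet as follow-up is lost

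*Combined protocol and SAP*

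**What the plan says.** Section 8 b) fixes the size: "The sample size is 75 fillings". Section 8 d) states that "an annual drop-out rate of 2% can be expected" and concludes: "Accordingly, three fillings could no longer be checked after 2 years".

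Section 8 e) sets the two later limits as counts: "Acceptance criterion for loss of vitality after 1 year: maximum 1 restored tooth" and "Acceptance criterion for filling replacement after 2 years: maximum 3 fillings". The 4-week hypersensitivity limit in the same item is given as a percentage together with a count. Section 8 c) declares the system suitable for the market if the criteria are met.

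On drop-outs, Section 8 k) says: "The recall data obtained up to the time of withdrawal from the study are used in the evaluation". Section 7.3 c) agrees. Both report drop-outs separately with their cause (CRF V), and both list treatment by an external dentist as an example of drop-out. Section 7.1 f) rules out any exchange of participants. Section 8 a) sees no need for special statistical methods, and no time-to-event, imputation or sensitivity analysis is described.

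The limits also appear among the working hypotheses. Sections 1 c) and 2 both give the replacement limit as a count: "After 2 years a maximum of 3 fillings should be replaced due to poor quality". For vitality, Section 1 c) gives one tooth, but Section 2 gives a rate: "The rate of loss of vitality after 1 year is maximum 1" percent.

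**The concern.** A ceiling on events is a clear rule only if the number at risk is known. Here a filling that is lost before an event is seen adds nothing to the count, so its effect is that of a surviving filling. The distortion has one direction: losing follow-up can only make the limit easier to meet. Three replacements pass equally whether 75, 72 or 60 fillings were examined, although the rates are 4.0%, 4.2% and 5.0%.

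The plan's own wording also allows loss to be linked to failure. A patient whose study filling fails may have it replaced by another dentist. Under Sections 7.3 c) and 8 k) that patient becomes a drop-out, and no rule says that the replacement still counts. At stake is a market-suitability decision that rests on ceilings as small as one and three events.

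**Working it through.** **Inputs.** 75 fillings (8 b); 2% annual drop-out and three fillings not checkable at 2 years (8 d); limits of 1 tooth at 1 year and 3 fillings at 2 years (8 e). The true replacement rates of 4%, 6% and 8%, and the case of 60 fillings followed, are assumptions chosen to show the range.

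**The plan's own figure.** Expected loss at 2 years is 75 × 2 × 0.02 = 3.00, or 75 × (1 − 0.98²) = 2.97 if compounded. The stated three is reproduced, leaving 72. Expected loss at 1 year is 75 × 0.02 = 1.5.

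**Chance of meeting the replacement limit.** P(X ≤ 3) for X binomial with n fillings followed and true rate p. This treats fillings as independent and takes the extreme case that no event is seen in a lost filling before it is lost.

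| Fillings followed | p = 4% | p = 6% | p = 8% |
|---|---|---|---|
| 75 (no loss) | 64.7% | 33.4% | 14.0% |
| 72 (planned loss) | 67.5% | 36.6% | 16.3% |
| 60 (assumed) | 78.1% | 51.1% | 28.3% |

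The planned loss moves the chance of passing by 2.8, 3.2 and 2.3 points. Following only 60 means losing 15 of 75 = 20% over two years, about five times the planned 4%; the shifts are then 13.4, 17.7 and 14.3 points.

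**Vitality limit.** P(X ≤ 1) at a true rate of 2% is 55.6% with 75 followed and 66.2% with 60. The pattern is the same.

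**Bounds when the limit is just met.** With 3 replacements seen and 3 fillings lost before any event:
- none of the lost fillings failed: 3/75 = 4.0%
- evaluable fillings only: 3/72 = 4.2% (exact 95% interval 0.9% to 11.7%)
- all of the lost fillings failed: 6/75 = 8.0%

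**Vitality wording.** One tooth in 75 is 1/75 = 1.33%, which exceeds 1%. One percent of 75 is 0.75, so a strict 1% limit allows no event, whereas Sections 1 c) and 8 e) allow one.

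**Two remedies that do not work well.**
- A hard limit at 3/72 = 4.17%. One further loss gives 3/71 = 4.23%, a fail, so the allowance drops from 3 to 2. At a true 4% the chance of passing falls from 67.5% (≤ 3 of 72) to 45.6% (≤ 2 of 71).
- Counting every lost filling as a failure. With three losses, only zero observed replacements pass. That has probability 0.98⁷² = 23% at a true 2% and 0.96⁷² = 5% at a true 4%.

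**The case against.** The case against has four parts.

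- **Earlier data are kept.** A replacement or loss of vitality recorded at 6 or 12 months counts even if the patient later leaves. This stands. A reader might infer that every lost filling is scored as a success; Sections 7.3 c) and 8 k) do not support that. The point concerns only fillings lost before an event is recorded.
- **Three expected losses and three allowed replacements.** A reader might take this equality for an error. It is a coincidence of two different quantities. Sections 1 c) and 2 tie the limit to replacement for poor quality, while drop-outs include unrelated extractions and changes in the opposing dentition. The equality serves only to show how far the bounds spread.
- **Size.** Section 8 d) bases the 2% on older comparable studies, and at that rate the shift is two to three points. This stands. No document supports a loss as high as the 60-filling case, which is illustrative.
- **A denominator is implied.** The number placed is fixed at 75, and Section 2 words the vitality limit as a rate. This helps little: the rate has no defined denominator and disagrees with the count in Section 8 e).

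What the objection leaves untouched is the external-dentist route. It does not depend on a high overall loss, and the plan has no rule for it.

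**Conclusion.** The concern holds in limited form. The two limits ignore the number of fillings examined, and loss before an observed event can only favour the product. At the plan's own loss rate, if loss is unrelated to outcome, this adds two to three percentage points to the chance of passing the replacement limit. It matters more if loss is well above plan or is related to failure; with three replacements seen and three fillings lost, the observed pass is compatible with anything from 4.0% to 8.0% of fillings placed.

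The probabilities assume independent fillings, although up to two per patient are allowed, and no event seen in a lost filling. The second assumption makes them upper bounds on the effect of loss unrelated to outcome. A reader might infer that the planned drop-out by itself makes the criteria invalid; the figures do not support that. These are secondary endpoints, but Section 8 c) includes them in the market decision, so the gap should be closed before the 1-year and 2-year results are judged.

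**What to change.** In Section 8 e), keep the stated counts as the criteria and add the following:

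1. With each count, report the number of fillings examined and the Kaplan-Meier cumulative proportion over all fillings placed, with a 95% interval: at 12 months for vitality, at 24 months for replacement. Censor each event-free lost filling at its last recall.
2. Count a replacement or endodontic treatment of a study tooth by an external dentist as an event, unless CRF V records a cause unrelated to the filling. Kaplan-Meier censoring assumes that loss is unrelated to outcome, so this rule is needed alongside it.
3. Add a sensitivity analysis that counts as failures those lost fillings whose drop-out cause is unknown or possibly related to the filling, leaving out unrelated extractions. State whether the acceptance verdict survives it.
4. Reconcile the 1% vitality limit in Section 2 with the one-tooth limit in Sections 1 c) and 8 e).

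The cost is some plan wording and a few lines of analysis on recall and drop-out records that the plan already collects; no extra visits are needed. The downside for the sponsor is a less favourable conclusion if losses prove high or related to failure.
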